3 DRUG INFORMATION

In this study, carvedilol will be administered twice daily to the intervention group. Carvedilol is currently approved by the FDA for indications that are unrelated to the current study. The following is a summary of the FDA label for carvedilol which can be found in the following link: https://www.accessdata.fda.gov/drugsatfda_docs/label/2005/020297s013lbl.pdf.

Carvedilol is a white to off-white powder with a molecular weight of 406.5 and a molecular formula of $C_{24}H_{26}N_2O_4$. Carvedilol is rapidly and extensively absorbed following oral administration, with absolute bioavailability of approximately 25% to 35% due to a significant degree of first-pass metabolism.

Following oral administration, the apparent mean terminal elimination half-life of carvedilol generally ranges from 7 to 10 hours. Plasma concentrations achieved are proportional to the oral dose administered. Carvedilol is more than 98% bound to plasma proteins, primarily with albumin. The plasma-protein binding is independent of concentration over the therapeutic range. Carvedilol is extensively metabolized. Less than 2% of the dose is excreted unchanged in the urine. The oxidative metabolites are further metabolized by conjugation via glucuronidation and sulfation. The metabolites of carvedilol are excreted primarily via the bile into the feces. Plasma concentrations of the active metabolites are about one-tenth of those observed for carvedilol and have pharmacokinetics similar to the parent. The primary P450 enzymes responsible for the metabolism of carvedilol in human liver microsomes are CYP2D6 and CYP2C9 and to a lesser extent CYP3A4, 2C19, 1A2, and 2E1. Since carvedilol undergoes substantial oxidative metabolism, the metabolism and pharmacokinetics of carvedilol may be affected by induction or inhibition of cytochrome P450 enzymes such as Rifampin, Cimetidine and Digoxin.

Indications for use of carvedilol are congestive heart failure, left ventricular dysfunction following myocardial infarction and hypertension. It is contraindicated in patients with bronchial asthma or related

bronchospastic conditions, in patients with hypersensitivity to any component of the product second- or third-degree AV block, sick sinus syndrome or severe bradycardia (unless a permanent pacemaker is in place), or in patients with cardiogenic shock or who have decompensated heart failure requiring the use of intravenous inotropic therapy. It is also not recommended in patients with clinically manifest hepatic impairment.

In terms of pregnancy and teratogenic effects, carvedilol is categorized in Pregnancy Category C. Studies performed in pregnant rats and rabbits given carvedilol revealed increased post-implantation loss in rats at doses of 300 mg/kg/day (50 times the MRHD as mg/m²) and in rabbits at doses of 75 mg/kg/day (25 times the MRHD as mg/m²). In rats the no-observed-effect level for developmental toxicity was 60 mg/kg/day (10 times the MRHD as mg/m²); in rabbits it was 15 mg/kg/day (5 times the MRHD as mg/m²). There are no adequate and well-controlled studies in pregnant women.

The most common side effects are:

Body as a Whole: allergy, malaise, hypovolemia, fever, leg edema.

Cardiovascular: fluid overload, postural hypotension, aggravated angina pectoris, AV block, palpitation, hypertension.

Central and Peripheral Nervous System: hypesthesia, vertigo, paresthesia.

Gastrointestinal: melena, periodontitis.

Liver and Biliary System: SGPT increased, SGOT increased.

Metabolic and Nutritional: hyperuricemia, hypoglycemia, hyponatremia, increased alkaline phosphatase, glycosuria, hypervolemia, diabetes mellitus, GGT increased, weight loss, hyperkalemia, creatinine increased.

Musculoskeletal: muscle cramps.

Platelet, Bleeding and Clotting: prothrombin decreased, purpura, thrombocytopenia.

Psychiatric: somnolence.

Reproductive, male: impotence.

Special Senses: blurred vision.

Urinary System: renal insufficiency, albuminuria, hematuria.

In clinical trials, carvedilol has been shown to cause bradycardia in about 2-9% of hypertensive patients. In clinical practice, if the pulse rate drops below 55 beats/minute, the dosage is typically reduced.

In the United States, the FDA recommend the starting dose of carvedilol to be 3.125 mg, twice daily for 2 weeks. Patients who tolerate a dose of 3.125 mg twice daily may have their dose increased to 6.25, 12.5, and 25 mg twice daily over successive intervals of at least 2 weeks. In clinical practice, patients should be advised that initiation of treatment and (to a lesser extent) dosage increases may be associated with transient symptoms of dizziness or lightheadedness (and rarely syncope) within the first hour after dosing. Thus, during these periods they should avoid situations such as driving or hazardous tasks, where

symptoms could result in injury. In addition, carvedilol should be taken with food to slow the rate of absorption. In Japan, a lower dose of carvedilol (2.5 mg twice daily) has been used and tested for clinical efficacy⁷⁴.

4 STUDY DESIGN

4.1 Description

The current study will be a double-blinded, placebo-controlled study in which Type 1 diabetic patients with hypoglycemia unawareness are randomized to either 1) placebo treatment, 2) 2.5mg carvedilol twice daily or 3) 3.125mg carvedilol twice daily. After enrollment, the participants will be placed on (blinded) CGM monitoring which will be continued until the end of the study. Additionally, participants will be provided with a glucometer to measure their blood glucose and for calibrating the CGMs during the study. One week after CGM placement, the participants will undergo the first hypoglycemic clamp study to obtain baseline measures of hypoglycemia frequency (from downloaded CGM data), hypoglycemia awareness scores and hormone responses. Following the initial clamp procedure, the patients will be randomized to either 4 weeks use of carvedilol or placebo. After the 4 weeks of treatment, the participants will undergo a second hypoglycemic clamp session. Patients will be hospitalized the night before each clamp study to ensure stable glucose levels.

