6.3 Duration of Therapy

The period of treatment is 4 weeks (28 days).

Subjects will be withdrawn or discontinued from the study if any of the following occurs:

- The subject withdraws consent for further participation in the clinical trial. At any time during the trial and without the need to provide a reason or rationale, a subject may choose to decline to participate further in the study. The subject will not suffer any consequences as a result.
- Subject is lost to follow-up despite efforts to contact them.
- Episodes of severe bradycardia and hypotension requiring hospitalization.

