8 STUDY CALENDAR

Period	Screening	Treatment Period			
		Intervention Phase (4 weeks)			
		Baseline CGM	1 st Hypoglycemic Clamp Study	Follow-Up	2 nd Hypoglycemic Clamp Study
Visit No.	1	2	3	4	5
Week ¹	-5 to -2	-2	0	1-2	4
Assessments					
Informed consent	X				
Inclusion/Exclusion criteria	X				
Demographics	X				
Vital signs	X		X	X	X
Physical Examination	X				
Pregnancy Test	X	X	X		X
ECG	X		X		X
Hematology/Chemistry/Urinalysis ²	X				
AE Assessment		X	X	X	X
Concomitant Medications	X	X	X	X	X
CGM and Glucometer		X ³	X	X	X ³
Fear Survey			X	X	X
Hypoglycemia Awareness Survey	X			X	X
Overnight Hospital Admission			X		X
Investigational Drug Treatment			X ⁴	X	X ⁴
Primary Objective Assessment			X		X
Secondary Objective Assessment			X		X

1. All screening procedures should be completed within 4 weeks of study enrollment (Visit 1), with the exception of laboratory tests which must be completed within 2 weeks, and pregnancy test which must be completed within 48 hours of screening (Visit 1). All visits within the “Treatment Period”, except the 2nd hypoglycemic clamp study, should occur within \pm 3 days of target date. The 2nd hypoglycemia clamp may be postponed up to 7 days due to hypoglycemia prior to the clamp study.
2. Hematology labs include CGC with differential and platelets; Chemistry labs include c-peptide, HbA1c, Hemoglobin, Albumin, Alkaline Phosphatase, Aspartate Aminotransferase, Alanine Aminotransferase, Total Bilirubin, Creatinine, Glucose, Potassium, TSH, Sodium and Urea Nitrogen; Urinalysis is a dipstick urinalysis including Protein, Hemoglobin and Glucose

3. The CGM is placed after enrollment and until the completion of the second hypoglycemic clamp study. Bayer Contour Next EZ[®] glucometer will be provided to participant and they will be required to use it to monitor their blood glucose and to calibrate the blinded CGMs.
4. The investigational drug treatment is to be started after the first hypoglycemic clamp study and completed on the day prior to the second hypoglycemic clamp study.

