9.10 The Clamp Procedure

Patients will be asked to reduce the dose of long-acting insulin 24 hours prior to the clamp study if applicable. The night before the clamp study, the subjects will be admitted into the CSC and the CGMs will be checked for hypoglycemia (reading <75-80mg/dl). We are setting this cut-off a little higher than the clinical definition of hypoglycemia (<70mg/dL) to ensure central mechanisms that are normally triggered by mild hypoglycemia are not activated⁷⁵. If hypoglycemia (<75-80mg/dL) is noted within 24 hours of beginning the clamp study, then the study will be delayed for one week. Qualifying subjects will be provided with a standardized low glycemic index meal to avoid fluctuations in blood glucose levels during the overnight fast. The CSC nursing staff will introduce an intravenous (antecubital vein) insulin drip in the subject and blood glucose levels will be maintained between 90-120mg/dl during the overnight fasting period. Blood glucose concentrations will be determined from a fingerstick using a point-of-care glucometer in order to titrate the insulin drip.

First Hypoglycemic Clamp: The next day, the patient will be asked to void their bladder prior to the start of the clamping procedure. The participant will then remain in bed in a supine position for the procedure. The participant will be asked to refrain from watching television during the procedure. A second catheter will be inserted into the contralateral hand vein for blood sampling and the sampling hand placed into a heated (~55°C) box to arterialize the blood. An ECG will also be connected to the subject to monitor heart electrical activity. Heart rate, blood pressure and ECG will be monitored every 15 minutes throughout the study. Prior to the drawing of each blood sample, the deadspace volume (~5-6ml) will be withdrawn into a syringe. A new syringe will be replaced onto the luer lock and the required blood volume drawn into new syringe. Following blood collection, the collected deadspace volume will be reinfused, followed by a saline infusion through the intravenous line to clear it of residual blood. Baseline blood samples (30mL) will be

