9.11.2 Secondary Objective Assessment

The secondary objective assessment will establish whether the frequency of CGM-determined hypoglycemic episodes differs during 4 weeks of carvedilol treatment compared to baseline and compared to the placebo-treated control group.

Patients will wear a blinded CGM that is installed 14 days prior the first clamp study and the device will continue to be worn throughout the entire study. These CGMs will be calibrated using the provided Bayer Contour Next EZ[®] glucometer. During the first clamp study, the follow-up visit and the second clamp study, data from the CGM will be downloaded and saved onto a secure server and exported into an Excel format for analysis. We will identify the number hypoglycemic excursions during the intervention period and compare this to the number of hypoglycemic episodes encountered during the 7-day period before the first clamp study, the “baseline” period. Comparisons between treatment groups at baseline and following the intervention period, as well as differences from baseline within each treatment group will be made.

Analysis of the CGM data will emphasize the number of hypoglycemic episodes as well as the duration and depth of the hypoglycemic episodes. A single hypoglycemic episode is defined as a glucose reading <70 mg/dL, followed by a reading ≥ 70 mg/dL, lasting at least 15 minutes or at least two readings below 70mg/dL over 15 minutes. If there is less than 30 minutes between two registered episodes of hypoglycemia these are considered as one episode.

We will also evaluate the answers to the fear surveys to determine whether those patients who are treated with carvedilol have a reduction in their fear of hypoglycemia compared to those on placebo.

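### CGM episode counts from a 28-day treatment period are compared with counts from a 7-day baseline without conversion to a rate, and the sections disagree on whether the CGM lead-in is 7 or 14 days

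*Combined protocol and SAP*

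**What the plan says.** **Length of the CGM lead-in.** Section 4.1 says "One week after CGM placement, the participants will undergo the first hypoglycemic clamp study". Section 9.11.2 says "Patients will wear a blinded CGM that is installed 14 days prior the first clamp study". The study calendar in section 8 puts the baseline CGM visit at week -2 and the first clamp at week 0, which agrees with 9.11.2. Section 9.8 says only that the device is placed after enrollment, so it does not settle the matter.

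**Baseline window and comparison.** Section 9.11.2 compares the number of excursions in the intervention period with "the number of hypoglycemic episodes encountered during the 7-day period before the first clamp study". It plans comparisons between groups at baseline and after the intervention, and differences from baseline within each group. Section 6.3 gives the treatment period as 28 days. Section 10 lists CGM hypoglycemia frequency as the secondary variable, to be analysed by ANOVA. Neither section mentions a rate, a denominator of wear time or a minimum amount of valid wear.

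**Timing rules that affect the windows.** Calendar footnote 1 allows treatment-period visits, apart from the second clamp, to move by 3 days either way. It also lets the second clamp be postponed by up to 7 days because of hypoglycemia. Under section 9.10, if low glucose "is noted within 24 hours of beginning the clamp study, then the study will be delayed for one week".

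**The concern.** The secondary question is whether CGM hypoglycemia falls from baseline on carvedilol, and whether it falls by more than on placebo. A count is comparable between two periods only if the periods are equally long or the count is divided by time observed. Here one period is four times the other. Followed as written, the within-group analysis would show a large rise in hypoglycemia in all three arms even if the drug did nothing, and it could hide a real reduction.

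The lead-in conflict adds to this. The baseline needs 7 days of wear, and one of the two stated lead-ins supplies exactly 7. Any early clamp or gap in the sensor record would then shorten the baseline for that patient, and a raw count would treat the shorter record as a lower burden of hypoglycemia.

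**Working it through.** The plan gives no figure to reproduce for this outcome: no CGM episode rate, no standard deviation and no effect size.

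**1. Raw counts over unequal periods**

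Inputs: baseline 7 days = 1 week (9.11.2); treatment 28 days = 4 weeks (6.3). Let r be a patient's true weekly rate, unchanged by treatment.

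- Expected baseline count: r × 1 = r.
- Expected treatment count: r × 4 = 4r.
- Ratio: 4r / r = 4, whatever r is.
- Raw change: 4r − r = 3r.
- If two arms differ by d per week at baseline and nothing changes, their mean raw changes differ by 4d − d = 3d. On a weekly-rate scale the difference in change is d − d = 0.

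If a postponed second clamp added its full 7 days to the counted period, the ratio would be 35/7 = 5. The plan does not say whether those days count.

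**2. Lead-in against the 7-day baseline**

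| Source | Nominal lead-in | Spare days beyond the 7 needed |
|---|---|---|
| 4.1 | 7 days | 7 − 7 = 0 |
| 9.11.2 | 14 days | 14 − 7 = 7 |
| Calendar, week -2 to 0 | 2 × 7 = 14 days | 7 |

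On the calendar's own schedule, a 3-day shift of the clamp gives 14 ± 3 = 11 to 17 days. If both visits shift, it is 14 ± 6 = 8 to 20 days. The 7-day window is always covered. On the 4.1 schedule, each day by which the clamp is early removes one baseline day.

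**3. What a 14-day baseline would gain**

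Assume Poisson counts and a stable true rate for each patient. With b baseline weeks, the sampling variance of the change in weekly rate is r/b + r/4.

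- b = 1: r + r/4 = 1.25r.
- b = 2: r/2 + r/4 = 0.75r.
- Reduction: 1 − 0.75/1.25 = 40%, for any r.

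That applies to an unadjusted change score. With adjustment for the baseline rate, the residual variance of the treatment-period rate is T + r/4 − T²/(T + r/b), where T is the between-patient variance of true weekly rates. The documents give neither r nor T. Assume r = 2.5 per week and a between-patient SD of 1 or 2 per week:

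- SD 1 (T = 1): b = 1 gives 1.625 − 1/3.5 = 1.339; b = 2 gives 1.625 − 1/2.25 = 1.181. Reduction 12%.
- SD 2 (T = 4): b = 1 gives 4.625 − 16/6.5 = 2.163; b = 2 gives 4.625 − 16/5.25 = 1.577. Reduction 27%.

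**The case against.** **The outcome may be meant as a rate.** Section 10 and the opening of 9.11.2 both speak of frequency, which can be read as episodes per unit of time. The plan also compares arms after the intervention, where all arms share the same nominal 28 days and no fourfold artefact arises. Both points are fair and limit the damage. But the sentence that says what will be computed compares numbers of episodes, within-group differences from baseline are explicitly planned, and section 10 adds no denominator. The rate reading needs to be written down.

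**Tempting stronger readings that the documents do not support**

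- *Baseline wear could be as short as 4 days.* This subtracts the 3-day visit tolerance from the one week in 4.1 (7 − 3). The tolerance belongs to the calendar, whose lead-in is 14 days, so the figure mixes two schedules that contradict each other. If visits are on target and no data are lost, the analysed baseline is the same last 7 days under either text.
- *Half the baseline record is wrongly thrown away.* Using the 7 days next to the clamp is a defined, fixed-length window and a defensible choice. The first week may be a run-in, though the documents do not say so.
- *A 14-day baseline would cut the variance by 40%.* That is a ceiling for a raw change score under Poisson counts. With baseline adjustment the gain is smaller, and clustering of episodes would make the Poisson assumption doubtful.
- *The 2-3 episodes per week in section 2 can be used to size the problem.* That figure is background on symptomatic episodes, whereas the outcome is CGM readings below 70 mg/dL in patients with impaired awareness. The factors of 4 and 3d do not depend on it.
- *Section 4.1 is the section in error.* Its one week matches the 7-day baseline in 9.11.2, just as the 14-day placement in 9.11.2 matches the calendar. The documents show a conflict, not which figure was intended.

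**Conclusion.** The point holds. As worded, the baseline comparison in 9.11.2 gives about a fourfold rise in episodes when nothing has changed, and it triples any chance baseline difference between arms in the raw change. With 7 patients per arm, some such difference is to be expected. These factors follow from the period lengths alone and assume only an unchanged rate and complete wear.

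The lead-in conflict is real but smaller. It matters if the 7-day lead-in is the one used and a clamp is early or sensor data are lost. Extending the baseline to 14 days is an optional improvement in precision: at most 40% of the sampling variance for a raw change score, and about 12% to 27% with baseline adjustment under the assumed rate and SDs.

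Only the secondary CGM outcome is affected. Symptom scores and hormone responses are not.

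**What to change.** 1. In 9.11.2 and section 10, express every CGM outcome (episodes, duration, time below range) per day of valid wear in both periods, and define a valid day. State whether days added by a postponed second clamp count.
2. Compare arms on the treatment-period rate, adjusting for the baseline rate. Within-group changes, if kept, should be changes in rate.
3. Reconcile 4.1 with 9.11.2 and the calendar, and state the intended lead-in. If the first of two weeks is a run-in, say so.
4. Optionally, use a fixed baseline window of up to 14 days ending at admission for the first clamp, which leaves out the overnight insulin infusion. Avoid using all days since placement: the delay rule in 9.10 would make the length of baseline depend on hypoglycemia, which is the outcome itself.

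Cost: items 1 to 3 are wording and a short analysis specification. The baseline covariate uses one residual degree of freedom (21 − 3 = 18 becomes 17). If 7 days is current practice and 14 is adopted, each patient wears the sensor for at most one more week.

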4.2 Dose Limiting Toxicity

Patients allocated to the drug treatment groups will receive a dose of either 2.5mg or 3.125mg of carvedilol twice daily. The goal is to use the lowest efficacious dose for improving hypoglycemia awareness in T1DM patients with little to no side effects. Our preclinical data suggests that at higher doses, β -blockers provide no benefits in terms of improving hypoglycemia awareness.

4.3 Number of Subjects

21 Type 1 diabetic patients with hypoglycemia unawareness will be recruited for the study. The 21 T1DM patients will be randomly allocated to one of the following treatments: 1) placebo (N=7), 2) 2.5mg carvedilol twice daily (N=7) or 3) 3.125mg carvedilol twice daily (N=7). Placebo will be taken twice daily.

4.4 Number of Study Centers

This is a single-center study being conducted at the University of Utah.

4.5 Study Duration

The enrollment of patients will begin in the late fall of 2018. We anticipate that the study procedures will begin in the fall of 2018 and continue until spring 2020. Data analysis and publication of the results are expected to be completed in the late spring or summer of 2020.

5 ELIGIBILITY CRITERIA

This checklist is used to determine subject eligibility; it should be completed for each subject, including review and signature by the enrolling investigator and filed in the subject research chart.

Subject ID: _____ Subject Initials: _____

5.1 Inclusion Criteria

Yes/No (a response of 'No' indicates the subject is **ineligible**)

1. _____ Type 1 diabetes for more than 5 years
2. _____ Age > 18 years
3. _____ Presence of impaired hypoglycemia awareness/unawareness
4. _____ Intensive insulin treatment as defined by multiple daily insulin injections (3 or more) or insulin pump therapy
5. _____ Negative pregnancy test
6. _____ Able to provide informed consent and willing to sign an approved consent form that conforms to federal and institutional guidelines.

5.2 Exclusion Criteria

Yes/No (a response of "Yes" indicates the subject is **ineligible**)

1. _____ Major medical disorders (including liver disease, cardiovascular disease, kidney disease, COPD, asthma, active malignancy or HIV)
2. _____ Overt diabetes complications (neuropathy, nephropathy, retinopathy)
3. _____ Anemia
4. _____ Current or recent use of beta-blocker therapy
5. _____ Use of diuretics
6. _____ Allergies or contraindications to beta-blockers or heparin
7. _____ Use of benzodiazepines
8. _____ Alcohol, drug or medication abuse
9. _____ Frequent use of acetaminophen

I verify that this subject meets all eligibility criteria for enrollment onto this study

Investigator Signature

Date

